11.4.2 Adverse events

All adverse events (AE) as documented by the physician(s) on the AE eCRF or on the SAE eCRF will be taken into account in the AE analysis. Information from other eCRF pages will be screened for possible AEs. However, events and symptoms which are related to a worsening of the underlying disease to be treated with anastrozole, will not be considered as (S)AEs in the statistical analysis.

Due to the different level of information related to the events, the AE analysis will be performed in two different ways:

- taking only adverse events from the corresponding AE and/or SAE section into account,
- taking adverse events from the AE and/or SAE section but also the additional events from other sections of the eCRF.

However, for all adverse events not documented in the AE and/or SAE section, no additional information (e.g. intensity, causality, etc.) as requested on the AE eCRF will be available.

General principles:

Only adverse events with a date/time of onset later or equal to the start date of the anastrozole therapy (or, if not exactly known, the date of 1st prescription of anastrozole) will be taken into account in the AE analysis. All AEs with a date/time of onset before this start date or with missing information on date/time of onset will be listed but not taken into account in the AE analysis.

To ensure consistency of AE and SAE data, a so-called reconciliation between adverse event information in the study data base and information in the Drug Safety data base of the sponsor will be performed before the start of the AE analysis.

All AEs as described by the participating physician(s) will be coded using the lowest level terms (LLT) from the latest installed version of the MedDRA Dictionary (V. 11.1 or higher).

For any AE as described by the physician(s) the lowest level term will be chosen that best matches or approximates the physician's actual description. These lowest level terms will be translated into more general terms [so-called preferred terms (PT)], which will be classified into a system organ class (SOC). This system organ class will be the primary system organ class as given in the MedDRA dictionary.

If a patient has experienced more than one AE and at least one of the AEs is considered by the physician as being related to the anastrozole therapy, the patient will be counted as having had a drug-related AE. The same AE (i.e., the same preferred term) reported more than once for a single patient will be counted as one AE. If an AE occurs more than once for a single patient, the AE with the highest reported causality ranking to anastrozole (worst case) will be used in the AE analysis.

An overview table will be presented with the number (and percentage) of patients with at least one AE, with at least one SAE, with AEs leading to treatment discontinuation, with drug-related AEs as well as the number of patients who died during the NIS.

Serious adverse events:

Patients with serious adverse events (SAEs) will be listed and the following variables will be included: SAE description (as reported by the physician), MedDRA 'preferred term', MedDRA 'primary system organ class', start/stop dates, start/stop days relative to the first day of administration of anastrozole, relationship to anastrozole according to the physician and outcome.

Incidence of adverse events:

The number (%) of patients with at least one AE will be presented in a number of frequency tables:

- by MedDRA primary system organ class,
- by MedDRA primary system organ class and per MedDRA ‘preferred term’ within the various MedDRA primary system organ classes.

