7. PROGRAM PLAN AND PROCEDURES

7.1 Overall design and flow chart

This is an open, multicentre NIS.

[figure not shown]
It is planned to enrol subjects into this NIS between Q1 2009 and Q1 2010. Based on the plan outlined below, it is assumed that the last subject will be enrolled in Q1 2010 and subsequently documented until Q4 2010.

The treatment with anastrozole can be stopped at any time.

Furthermore it is expected, that the last completed eCRF will be filled in Q4 2010. It is planned to close all centres until end of Q1 2011 (i.e. the fees for all participating centres are paid).

Treatment with Anastrozole

Study duration

*or at point of treatment discontinuation

Evaluation period

Information to patients: study start, weeks 1, 3, 5, 8, 12, 20

- 1 The start of the adjuvant treatment with anastrozole is defined by the date of the first tablet intake. If this date is not available, the date of first prescription will be taken.
- 2 The end of participation in this NIS is defined as recurrence or death or withdrawal of informed consent is documented via WBDC. Patients who stop endocrine therapy (i.e. do not take further treatment) or patients who switch to an adjuvant endocrine therapy with tamoxifen or a different aromatase inhibitor or patients considered 'lost to follow-up' (i.e.: can no longer be contacted) will be documented as premature terminations. Otherwise this NIS terminates after completion of 12 (15) months observation period (12 respectively 15 months observation period results from time slot for inclusion, minimum 3 and maximum 6 months of anastrozole therapy prior to enrolment)

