8.3.1.2 Documentation of AE

All adverse events occurring during the observational period should be documented on the corresponding subject-related AE CRFs. However, events and symptoms which are related to a worsening of the underlying disease to be treated with anastrozole should not be documented as AE.

For each AE, the following information should be given:

- description of adverse event,
- start date of AE,
- stop date of AE,
- maximum intensity of AE [mild, moderate, severe],
- action taken on anastrozole [none, dose reduction, temporarily stopped, stopped],
- outcome [recovered, not yet recovered, permanent disability, death, unknown],
- causality/relationship to anastrozole [no, yes],
- AE serious [no, yes]

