9. CONDUCT OF THE NIS AND QUALITY ASSURANCE

Before the start of the NIS, each participating physician will be informed in detail about the objectives design and conduct of this NIS, the collection and handling of Informed Consent, the WBDC system, the handling of serious AEs, contact personnel and all other relevant aspects of this NIS. Each participating centre will receive a binder containing the necessary documents and information.

The participation of the physician must be confirmed by signing and dating the project-specific contract between the centre and AstraZeneca GmbH. This contract needs to be signed off by the following persons: participating physician and the AZ representative. The contract needs to be signed in two copies. One signed copy will be retained by the centre and the second signed copy will be filed by AstraZeneca.

Upon completion of the eCRF the investigator declares using a electronic signature form that all data recorded for a patient has been reviewed and are accurate. The digital signature comprises: i. time stamp (date and time of signature), ii. user details (user name and password). The WBDC system is compliant with the FDA (Food and Drug Administration) Code of Federal Regulations (21 CFR Part 11) Electronic Records; Electronic Signatures.

The end of this NIS is defined as the date when the last patient completed the visit scheduled nine months after start of the study.

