11. STATISTICAL METHODS AND DETERMINATION OF SAMPLE SIZE

The statistical analysis and reporting of this NIS will be performed by DSH statistical services under the supervision of and in close collaboration with AstraZeneca GmbH.

This section is focused on the first statistical analysis, i.e. after all patients were observed for at least three months. The final statistical analysis (after all patients were observed for 9 months) will be performed in the same way, but using the data in a cumulative way.

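### AE incidence is counted from the first tablet, but patients enter after 3 to 6 months on drug, so one crude percentage mixes retrospective and prospective collection

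*Protocol*

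**What the plan says.** **Analysis rule.** Protocol 11.4.2 counts "Only adverse events with a date/time of onset later or equal to the start date of the anastrozole therapy" or, if that date is not exactly known, the date of first prescription. Events with a missing onset date are listed but not counted. The output is the number and percentage of patients with at least one AE, overall and by MedDRA class and preferred term, without time intervals. The overview table also has a row for AEs leading to treatment discontinuation.

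**Documentation rule.** Protocol 8.3.1.2 states: "All adverse events occurring during the observational period should be documented on the corresponding subject-related AE CRFs". Section 8.3.1.3 uses the same period for SAE reporting, whereas 8.3.1.1 defines an SAE by the anastrozole treatment period.

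**Length of observation.** The flow-chart footnote in 7.1 says "Otherwise this NIS terminates after completion of 12 (15) months observation period" and explains that "12 respectively 15 months observation period results from time slot for inclusion, minimum 3 and maximum 6 months of anastrozole therapy prior to enrolment". Section 11 places the final analysis "after all patients were observed for 9 months". Section 9 says "The end of this NIS is defined as the date when the last patient completed the visit scheduled nine months after start of the study".

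**Entry.** Sections 6 and 6.1 require at least three and at most six months of anastrozole before enrolment.

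**Forms.** The schedule in 7.2 marks the AE/SAE module at study start and at each follow-up. The baseline list in 8.1.2 asks whether arthralgia has occurred since anastrozole began, but lists no such question for other events. The follow-up list in 8.1.3 has a general AE item. Section 8.1.3 also dates the 3, 6 and 9 month documentation in two ways: from study start in one block, and by months of endocrine therapy in the next.

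**The concern.** The time origin of the analysis lies three to six months before anyone is under observation. After enrolment, the follow-up form asks about AEs every three months. Before enrolment, an AE other than arthralgia enters the data only if patient or physician recalls it and the site decides it belongs in the study-start module. Whether it belongs there depends on what *observational period* means, and 8.3.1.2 and 8.3.1.3 do not say. Sites that take the period from first tablet, as the 7.1 footnote suggests, and sites that take it from study start, as Section 11 suggests, would deliver different data into the same numerator over the same denominator.

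A second loss cannot be repaired by recall. A woman who stopped anastrozole before month 3 because of an AE can never enrol. This bears most directly on the row for AEs leading to discontinuation.

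At stake is the safety and tolerability objective: a reader would take the tabulated percentage as AE incidence since the start of treatment.

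**Working it through.** **1. Reproduce the plan's own figure.** Months on drug before enrolment plus months of study follow-up:
- shortest: 3 + 9 = 12 months
- longest: 6 + 9 = 15 months

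This matches the 12 (15) months in 7.1 exactly. The 9 months in Sections 9 and 11 are the same schedule counted from study start.

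**2. Share of the AE counting window before enrolment**, for a patient who reaches the last visit:
- entry at 3 months: 3/12 = 25%
- entry at 6 months: 6/15 = 40%

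**3. What the pre-enrolment share could do to the percentage.** The protocol gives no AE rates, so this is an illustration. Assumptions: constant hazard, true incidence p over the full span T, and nothing captured before enrolment. Then recorded incidence = 1 − (1 − p)^(9/T).

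| True incidence p over full span | T = 12 (3 months missed) | T = 15 (6 months missed) |
|---|---|---|
| 10% | 7.6% | 6.1% |
| 30% | 23.5% | 19.3% |
| 50% | 40.5% | 34.0% |

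For p = 30%: 1 − 0.70^0.75 = 0.235 and 1 − 0.70^0.60 = 0.193. With complete retrospective capture the loss is zero. For p = 30% the recorded value therefore lies between 23.5% and 30% at T = 12, and between 19.3% and 30% at T = 15, depending on capture.

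**4. Unequal span alone.** Even with perfect capture, the window differs by patient. At one constant hazard, 30% over 12 months corresponds to 1 − 0.70^(15/12) = 36.0% over 15 months. The crude percentage pools these spans.

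**5. Women who stopped before entry.** Suppose, again as an illustration, that a fraction q stop before they can enrol, that 80% of them had an AE, and that 30% of the others did. Incidence among all starters is 0.8q + 0.3(1 − q):
- q = 5%: 32.5%
- q = 10%: 35%

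In both cases the study would see 30%.

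**6. Direction.** Steps 3 and 5 both lower the recorded figure relative to incidence since first tablet. Neither can be sized from the protocol.

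**The case against.** **The durations agree.** A reader might infer that 12 (15) months in one section contradicts 9 months in others. The documents do not support that: the 7.1 footnote explains the difference, and the sums agree. Nor is the start of the AE analysis undefined, since 11.4.2 states it. Because 7.1 is the only place that spells out the observation period, 8.3.1.2 can be read in the same sense, and both rules then start at first tablet. That stands as one possible reading, but no cross-reference makes it binding. Section 11 counts observation from study start, and the two clocks in 8.1.3 add to the doubt.

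**Early events are partly captured.** The AE/SAE module is open at study start, arthralgia is asked about explicitly, and 11.4.2 screens other eCRF pages and analyses AEs with and without the events found there. The patient's start questionnaire also contains a side-effect scale. This stands against any claim that nothing is recorded before entry, and the problem chiefly concerns AEs other than arthralgia. But undated events found by screening are not counted, and 11.4.2 draws its AEs from the eCRF, not from the patient questionnaire.

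**The size is not known.** A reader might take the table above as a measured understatement. It is not: the incidences, the hazard shape and zero capture are all assumed. Nor is any AE table by early month planned, so the effect would fall on the overall percentages.

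**The consequence is limited.** Safety is a secondary, purely descriptive objective, and the onset dates allow a split later. The analysis can indeed be split. However, what sites record before enrolment is settled by the protocol and eCRF, and an analysis plan cannot recover events that were never asked for.

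**Conclusion.** The point holds in a limited form. For patients who complete follow-up, a quarter to two fifths of the AE counting window precedes enrolment. AE collection there has no listed prompt except for arthralgia, and early stoppers are excluded by the entry criteria. The term that governs what sites document has no fixed origin. The planned percentage therefore mixes retrospective and prospective collection over spans of 12 to 15 months, and is likely understated as incidence since first tablet.

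The 25% and 40% follow from the protocol's own figures and assume that the patient reaches the 9-month visit. The direction assumes only that recall is incomplete or that some women stopped early because of AEs. The amount is not determined by the document and could be small for events fully recorded at study start.

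**What to change.** - **Sections 7.1, 8.3.1.2 and 8.3.1.3:** define the AE observational period once, with a start and an end, and state whether AEs from before enrolment are to be collected retrospectively. Bring the SAE definition in 8.3.1.1 into line.
- **Section 8.1.3:** reconcile the two follow-up clocks.
- **Section 11.4.2, main table:** present AEs with onset or worsening from study start as the prospective table. Label it as covering up to 9 months in patients who had already taken anastrozole for 3 to 6 months.
- **Section 11.4.2, supporting tables:** tabulate AEs dated between first tablet and study start separately as retrospective, and show the combined figure as supportive. Dropping the earlier events without the combined figure would be debatable, because it would hide events that were recorded.
- **Interpretation:** state that women who stopped before month 3 are not represented. No table can correct for this.

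The cost is wording in these sections, one extra table and a headline percentage over a shorter window. The split uses AE start dates already required by 8.3.1.2 and needs no additional patients.

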11.5 Justification of sample size

Based on previous data, it can be assumed that a patients’ compliance will decrease to approximately 50% during the first year of antihormone therapy, a difference in patients’ compliance of 6% will be judged clinically relevant. In order to recognize a statistically significant difference of 6% between two groups or between different time points 1119 patients are required per group or time point.

In the following table the sample size which is needed to detect a difference of 6% is presented with the corresponding odds ratios starting with an event rate of 44% for a standard group.

Two group continuity corrected chi-square test of equal proportions (odds ratio = 1) (equal n's, 2-sided test, $\alpha= 0.05$, Power = 80%)

Group 1 proportion, π_1		I
0,44	Proportion, π_2	0,5
	Odds ratio, $\psi = \pi_2 (1 - \pi_1) / [\pi_1 (1 - \pi_2)]$	1,273
	n per group	1119

nQuery Advisor 7.0

In a newly performed study a mean arthralgia score of 4 was found with a standard deviation of 1.86. Assuming a standard deviation (sd) of 2 and a difference of 10% between 2 groups a sample size of 394 in each group will have 80% power to detect a difference in means of - 0,4 (the difference between a Group 1 mean, μ_1 , of 4 and a Group 2 mean, μ_2 of 4,4) assuming that the common standard deviation is 2 using a two group t-test with a 0,050 two-sided significance level.

In the following table the sample size which is needed to detect a difference of 10% in the arthralgia score is shown for the t-test.

Comparison of equal means (2-sided test, $\alpha= 0.05$, Power = 80%)

	t-test
Group 1 mean, μ_1	4,000
Group 2 mean, μ_2	4,400
Difference in means, $\mu_1 - \mu_2$	-0,400
Common standard deviation, σ	2,000
Effect size, $\delta = \mu_1 - \mu_2 / \sigma$	0,200
n per group	394

nQuery Advisor 7.0

Based on previous non-interventional trials, approximately 25 to 40% of the patient documentation will not be accessible. Therefore, assuming a drop-out rate of 30%, 3212 patients will be enrolled to ensure a sufficient number of evaluable patients.

12. ETHICS

12.1 Ethics review

The observation plan, the final version of the Informed Consent Form and all written information material for patients must be approved or given a favourable opinion in writing by an Ethics Committee as appropriate. The sponsor will notify other Ethics Committees, which are responsible for the participating centres, about this NIS and will provide a copy of the master EC approval.

The sponsor is responsible for informing the Ethics Committee of any amendments in the observation plan, the Informed Consent Form or the written information material for patients in accordance with local requirements. In addition, the Ethics Committee must approve all advertising used to recruit patients for the program.

12.2 Patient data protection

The Informed Consent Form will incorporate wording that complies with relevant data protection and privacy legislation. Pursuant to this wording, patients will authorise the collection, use and disclosure of their NIS data by the investigator and by those persons who need that information for the purposes of the NIS. Pursuant to this wording, patients will agree to the collection and use of their names and addresses for the duration of this NIS.

The Informed Consent Form will explain that NIS data will be stored in a computer database, maintaining confidentiality in accordance with national data legislation. All data computer processed by [redacted] or AstraZeneca will be identified by randomisation number. It will also be explained that [redacted] will keep a copy of the signed Informed Consent Form and will store patient names and addresses in a computer database until the end of this NIS, and

that the sponsor will not have access to these data and that copies will be destructed and electronic data will be deleted at the end of this NIS (for further details see Section 7.3 and 10.1).

13. ARCHIVING

After completion of this NIS all collected and anonymous data (patient questionnaires and database set) will be handed over by _____ to AstraZeneca. AstraZeneca is responsible for archiving the data according to local legal requirements and AstraZeneca SOPs.

